#### **10.5.3 Resource utilization**

Summary statistics will be provided by treatment group on hospital length of stay (total and per ward) for the initial and subsequent hospitalizations, as well as procedures rendered during these hospitalizations,. Additional information will be provided in the Statistical Analysis Plan.

#### **10.5.4 Health-related Quality of Life**

Health related quality of life assessments will not be collected in this study.

#### **10.5.5 Pharmacokinetics**

Pharmacokinetics will not be collected in this study.

#### **10.5.6 Pharmacogenetics/pharmacogenomics**

Not applicable.

#### **10.5.7 Biomarkers**

Biological markers will be measured in a subset of patients. Summary statistics for the baseline values, the post-baseline values, and the change from baseline will be provided by treatment group for the FAS and Safety Set.

#### **10.5.8 PK/PD**

Not applicable.

## 10.6 Interim analyses

It is planned to establish an external and Independent Data Monitoring Committee (DMC) to monitor patient safety data on a regular basis during the course of the study. For this study, it is likely DMC will review safety data in a regular frequency, e.g., every six months. DMC may request additional safety data review. Such safety analyses do not inflate the type I error for the primary efficacy hypothesis testing and thus require no multiplicity adjustments.

It is planned to have one formal interim efficacy analyses. The cut-off for this interim analysis is planned when the information fraction (number of confirmed CV deaths relative to the targeted total number of confirmed CV death at the study completion) of 60% is achieved. Some adjustment to the time of interim analysis may be made to coincide with the regular DMC meetings. One-sided tests will be performed and appropriate statistical adjustments for the interim analysis actually performed will be made to ensure the overall one-sided type I error of 0.02 (Lan-DeMets spending function to match an O'Brien-Fleming stopping boundary). For the interim analysis, the analysis dataset will comprise all patients who were randomized before the cut-off date.

The trial may only be concluded early for efficacy, if a significant difference between two treatment arms for the number of CV deaths is achieved by crossing the pre-specified boundary (irrespective of WHF results) at interim analysis and the overall risk/benefit profile is considered positive. Interim analysis will be performed by an external independent statistician at an external data analysis center, who will not be involved in the study conduct. The results will be reviewed by the independent DMC. Investigators and others who are involved in the conduct of the trial and in the analysis of the final trial results, or who have contact with study centers, will remain blinded to the treatment codes and interim analysis results until all monitoring decisions have been made and the database has been locked for final analysis.

Additional details of the interim analysis plan for efficacy and safety will be described in the DMC charter.

## 10.7 Sample size calculation

The alpha ( $\alpha$ ) level of 5% is split to CV death at 4% and to WHF at 1%. The sample size calculation is based on the CV death endpoint. This is an event-driven trial with fixed maximum duration of 180 day follow-up period for each patient. In the sample size calculation, the 180-day CV death rate is assumed to be 9.0% in the placebo group, which is about 80% of 11.3% of all cause death observed in the placebo group in the RELAX-AHF study.

[REDACTED] This sample size accounts for one planned efficacy interim analysis when 60% of CV deaths have been accrued, using the Lan-DeMets spending function and an O'Brien-Fleming (OF) stopping boundary.

The interim analysis will be performed when 329 CV deaths are accrued. At the interim analysis, if Z-score of 2.786 (one-sided nominal  $p = 0.0027$ ) is observed, which corresponds to HR of 0.735 (at least 26.5% RRR), the DMC may recommend to stop the study due to crossing the boundary. If there is no stopping at the formal efficacy interim analysis, the final analysis will need to have a Z-score of 2.072 (one-sided nominal  $p = 0.0192$ ), which corresponds to HR

of 0.838 (at least 16.2% RRR), to declare a significant study. (East ® 5.4.2, Cytel Inc., Cambridge MA, 2010).

If the observed overall event rate of the CV death endpoint during the course of the trial is much lower than expected based on the design assumptions (assessed on a blinded basis), adjustments may be made to the number of patients to be randomized in order to achieve the required number of events in the pre-planned timeframe (180 days) and thus to preserve the target study power.

For the sample size of 6,800, the unconditional power for the WHF endpoint and all three key secondary endpoints under various HRs (mean difference for Length of Stay) are summarized below in [Table 10-1](#) and [Table 10-2](#):

**Table 10-1 Assumed effect sizes for worsening heart failure and the key secondary efficacy variables on power calculation**

	Assumed HR or mean difference
Worsening Heart Failure (placebo rate: 12.2%)	0.70
	0.80
All cause death (placebo rate: 11.3%)	0.80
	0.816
	0.83
Length of Stay (mean ±SD between placebo and serelaxin: 0.9 ±9.6 day)	0.9 day
	0.7 day
CV death or HF/RF rehospitalization (placebo rate: 34.1%)	0.85
	0.88

Note: Assumed placebo rates for all cause death and WHF and mean difference (mean ± SD) in LOS between serelaxin and placebo were based on RELAX AHF study; placebo event rate of CV death or HF/RF rehospitalization was estimated to be 34.1% by assuming an exponential distribution with the same hazard as that observed through Day 60 in RELAX AHF study.

**Table 10-2 Powers (unconditional) of primary and key secondary variables on selected scenarios**

A) All cause death

Scenarios of effect sizes	All cause death Day 180*
All-cause death (HR=0.80); WHF (HR=0.70)	83
All-cause death (HR=0.816); WHF (HR=0.70)	77

All-cause death (HR=0.82); WHF (HR=0.70)	70
All-cause death (HR=0.80); WHF (HR=0.80)	82
All-cause death (HR=0.816); WHF (HR=0.80)	76
All-cause death (HR=0.82); WHF (HR=0.80)	70

Note: The true HR for CV death is assumed to be 0.78 in all scenarios.

\*Power if one or both of the two primary variables are significant.

B) CVD, WHF, LOS and CVDR

Scenarios of effect sizes	CV death Day 180	WHF Day 5	LOS	CV death or HF/RF hosp.	Reject All
WHF (HR=0.7) – LOS (0.9 days) – CVD/rehosp (HR=0.85)	82	99	93	93	77
WHF (HR=0.7) – LOS (0.9 days) – CVD/rehosp (HR=0.88)	82	99	92	79	68
WHF (HR=0.7) – LOS (0.7 days) – CVD/rehosp (HR=0.85)	82	99	78	93	69
WHF (HR=0.7) – LOS (0.7 days) – CVD/rehosp (HR=0.88)	82	99	77	77	60
WHF (HR=0.8) – LOS (0.9 days) – CVD/rehosp (HR=0.85)	82	82	87	87	68
WHF (HR=0.8) – LOS (0.9 days) – CVD/rehosp (HR=0.88)	82	82	86	73	59
WHF (HR=0.8) – LOS (0.7 days) – CVD/rehosp (HR=0.85)	82	81	73	86	60
WHF (HR=0.8) – LOS (0.7 days) – CVD/rehosp (HR=0.88)	81	81	72	72	53

Note: The true HR for CV death is assumed to be 0.78 in all scenarios.

Note: The power for the WHF endpoint is approximated based on logrank test, but the analysis will be based on Gehan-Wilcoxon test.

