## Protocol synopsis

Protocol number	CRLX030A2301
Title	A multicenter, randomized, double-blind, placebo-controlled phase IIIb study to evaluate the efficacy, safety and tolerability of Serelaxin when added to standard therapy in acute heart failure patients
Brief title	Efficacy, safety and tolerability of Serelaxin when added to standard therapy in acute heart failure
Sponsor and Clinical Phase	Novartis/3b
Investigation type	Biologic/Vaccine
Study type	Interventional
Purpose and rationale	
The purpose of this study is to evaluate the efficacy, safety and tolerability of intravenous infusion of 30 µg/kg/day serelaxin administered by body weight category (Table 5-3) for 48 hours, when added to standard therapy, in approximately 6,800 acute heart failure (AHF) patients. Efficacy will be determined based on the relative reduction in CV death, worsening heart failure and other clinical outcomes through a follow-up period of 180 days, as compared to placebo.
 
The rate of mortality in AHF remains high despite contemporary standard-of-care management, which has not changed significantly in the last 10 years, and represents a key unmet need for AHF patients. In the RELAX AHF trial a clinically and statistically significant 37% reduction in both CV and all-cause mortality through Day 180 were seen. Data from this study is intended to replicate the reduction in mortality in AHF patients observed in the RELAX AHF trial. The reduction in worsening heart failure through Day 5 is a potential efficacy benefit which is evolving among the scientific community as an increasingly clinically relevant treatment goal of AHF. Following initial stabilization, in-hospital WHF occurs in 10- 30% of hospitalized patients reflecting a severe manifestation of the AHF disease continuum requiring immediate intensification of rescue therapy (Torre-Amione et al 2009, Cotter et al 2010, Metra et al 2010a, Teerlink et al 2013) and represents another key unmet need for AHF patients.

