## **1.2 Purpose**

This is a multicenter, randomized, double-blind, placebo-controlled study to evaluate the efficacy, safety and tolerability of intravenous infusion of 30 µg/kg/day serelaxin for 48 hours, when added to standard therapy, in approximately 6,375 AHF patients. Efficacy will be determined based on the relative reduction in CV death and other clinical outcomes including all-cause mortality through a follow-up period of 180 days, as compared to placebo. Data from this study is intended to replicate the reduction in mortality in AHF patients observed in the RELAX-AHF trial.

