In addition to the core study, ECG, laboratory and biomarker substudies will be conducted.

- At least 500 patients from selected centers will participate in an ECG substudy. ECGs will be performed at Baseline and at the end of study drug infusion.
- At least 1600 patients from selected centers will participate in a laboratory substudy. Safety laboratories will be collected at Baseline, daily while hospitalized up to Day 5, Discharge and Day 14. Patients discharged prior to Day 5 will return to the hospital/clinic for Day 5 procedures.
- At least 1600 patients from selected centers participating in the laboratory substudy will also participate in the biomarker substudy. Biomarkers will be collected at Baseline, Days 2, and 5, Discharge, and Day 14. Patients discharged prior to Day 5 will return to the hospital/clinic for Day 5 procedures.

Based on sample size calculations based on RELAX-AHF, approximately 6,800 randomized AHF patients will be required to accrue the number of events during the 180-day follow-up

period necessary to reach the primary efficacy endpoint. Once randomized, all randomized patients will be followed to 180-day.

There will be one interim analysis at 60% of the accrued numbers of confirmed CV deaths (see details in [Section 10.6](#) and [Section 10.7](#)). If following the interim analysis, the trial is concluded early for efficacy, all ongoing randomized patients will be followed for 180 days.

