## 4 Population

The study population will consist of male and female patients ( $\geq 18$  years old) admitted to the hospital for AHF, with systolic BP  $\geq 125$  mmHg, and mild-to-moderate renal impairment. It is aimed to randomize approximately 6,800 patients [REDACTED]

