2.5 Sample size and power considerations

The alpha (α) level of 5% is split to CV death at 4% and to WHF at 1%. The sample size calculation is based on the CV death endpoint. This is an event-driven trial with fixed maximum duration of 180 day follow-up period for each patient. In the sample size calculation, the 180-day CV death rate is assumed to be 9.0% in the placebo group, which is about 80% of 11.3% of all cause death observed in the placebo group in the RELAX-AHF study.

The interim analysis will be performed when 329 CV deaths are accrued. At the interim analysis, if Z-score of 2.786 (one-sided nominal $p = 0.0027$) is observed, which corresponds to HR of 0.735 (at least 26.5% RRR), the DMC may recommend to stop the study due to crossing the boundary. If there is no stopping at the formal efficacy interim analysis, the final analysis will need to have a Z-score of 2.072 (one-sided nominal $p = 0.0192$), which corresponds to HR of 0.838 (at least 16.2% RRR), to declare a significant study. ([contact], Cytel Inc., Cambridge MA, 2010).

If the observed overall event rate of the CV death endpoint during the course of the trial is much lower than expected based on the design assumptions (assessed on a blinded basis), adjustments may be made to the number of patients to be randomized in order to achieve the required number of events in the pre-planned timeframe (180 days) and thus to preserve the target study power.

For the sample size of 6,800, the unconditional power for the WHF endpoint and all three key secondary endpoints under various HRs (mean difference for Length of Stay) are summarized in the tables below:

Table 2-10 Assumed effect sizes for worsening heart failure and the key secondary efficacy variables on power calculation

	Assumed HR or mean difference
Worsening Heart Failure (placebo rate: 12.2%)	0.70
	0.80
All cause death (placebo rate: 11.3%)	0.80
	0.816
	0.83
Length of Stay (mean ±SD between placebo and serelaxin: 0.9 ±9.6 day)	0.9 day
	0.7 day
CV death or HF/RF rehospitalization (placebo rate: 34.1%)	0.85
	0.88

Note: Assumed placebo rates for all cause death and WHF and mean difference (mean + SD) in LOS between serelaxin and placebo were based on RELAX AHF study; placebo event rate of CV death or HF/RF rehospitalization was estimated to be 34.1% by assuming an exponential distribution with the same hazard as that observed through Day 60 in RELAX AHF study.

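### The all-cause-death power of 70% is labelled HR 0.82 but belongs to HR 0.83, and Protocol Section 1.2 still plans 6,375 patients instead of 6,800

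*Protocol*

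**What the plan says.** **Assumed effects.** Protocol Section 10.7, Table 10-1, has an entry "All cause death (placebo rate: 11.3"%) with hazard ratios 0.80, 0.816 and 0.83. SAP Section 2.5, Table 2-10, repeats them. The SAP text introducing the tables reads "For the sample size of 6,800, the unconditional power for the WHF endpoint and all three key secondary endpoints".

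**Reported powers.** Protocol Table 10-2 A and SAP Table 2-11 A use 0.80, 0.816 and 0.82. The rows in question are "All-cause death (HR=0.82); WHF (HR=0.70") and "All-cause death (HR=0.82); WHF (HR=0.80"), each with 70%. The full printed sequence is 83, 77, 70 with WHF hazard ratio 0.70, and 82, 76, 70 with WHF hazard ratio 0.80. A footnote says these are powers given that at least one primary variable is significant; another sets the CV-death hazard ratio at 0.78 throughout.

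**Sample size.** Protocol Section 1.2 describes the infusion "for 48 hours, when added to standard therapy, in approximately 6,375 AHF patients". Elsewhere the size is 6,800: the synopsis has "in approximately 6,800 acute heart failure (AHF) patients", Section 3.1 has "approximately 6,800 randomized AHF patients will be required to accrue the number of events", and Section 4 has "It is aimed to randomize approximately 6,800 patients". Protocol Section 10.7 and SAP Sections 2.4 and 2.5 also use 6,800.

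**The concern.** The assumption table and the power table in each document should cover the same scenarios, and they do not: 0.83 has no power row, and 0.82 has a power row but is not among the assumptions.

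The printed powers also do not move smoothly with the labels. Power falls 6 points (83 to 77) when the hazard ratio moves by 0.016, then 7 points (77 to 70) when the label moves by only 0.004. The second block does the same (82, 76, 70).

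At stake is the accuracy of the stated power for a key secondary mortality endpoint. A reader who takes the row at face value will credit hazard ratio 0.82 with too little power. In Section 1.2, a reader meets a planned size that the rest of the protocol contradicts.

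**Working it through.** **Inputs from the documents**
- 6,800 patients, 1:1, so 3,400 per arm (Protocol Sections 5.2 and 10.7).
- Placebo 180-day all-cause death rate 11.3% (Table 10-1).
- All-cause death tested at full two-sided alpha, 0.05, if CV death or WHF is significant (Protocol Section 10.5.1; SAP Section 2.2.6.4).
- For the gate: CV-death hazard ratio 0.78, placebo rate 9.0%, looks at 60% and 100% of events with Z bounds 2.786 and 2.072; WHF placebo rate 12.2%, one-sided 0.005, logrank approximation (as the table note states).

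**Step 1: power before the gate**

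Deaths under proportional hazards: d = 3400 × [0.113 + 1 − 0.887^HR].

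Power = Φ( (√d / 2) × ln(1/HR) − 1.96 ).

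| HR | d | (√d/2) × ln(1/HR) | minus 1.96 | Power | Printed (WHF HR 0.70 / 0.80) |
|---|---|---|---|---|---|
| 0.80 | 695.2 | 2.942 | 0.982 | 83.7% | 83 / 82 |
| 0.816 | 701.1 | 2.692 | 0.732 | 76.8% | 77 / 76 |
| 0.82 | 702.6 | 2.630 | 0.670 | 74.9% | 70 / 70 |
| 0.83 | 706.3 | 2.476 | 0.516 | 69.7% | no row |

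The 0.80 and 0.816 rows reproduce the WHF 0.70 column within one point, which supports the method. Solving for exactly 70% gives HR 0.8295. Before the gate, only hazard ratios from 0.8285 to 0.8304 give a power that rounds to 70%.

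**Step 2: apply the gate**

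The printed figures are gated, so the gate was simulated (4,000,000 replicates per case). Two assumptions are not in the documents. The WHF statistic is taken as independent of the other two. The correlation ρ between the all-cause-death and CV-death statistics is varied, with √(547/703) = 0.88 as a guide (547 expected CV deaths out of 703 deaths).

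*WHF HR 0.70.* The gate almost always opens. For any ρ from 0 to 0.95, power is 74.7–74.9% at HR 0.82 and 69.5–69.7% at HR 0.83. The unknown correlation does not matter here.

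*WHF HR 0.80.*

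| ρ | HR 0.80 | HR 0.816 | HR 0.82 | HR 0.83 |
|---|---|---|---|---|
| 0.8 | 80.9 | 74.9 | 73.2 | 68.4 |
| 0.9 | 81.5 | 75.6 | 73.9 | 69.1 |
| 0.95 | 81.9 | 76.0 | 74.3 | 69.5 |
| Printed | 82 | 76 | 70 | no row |

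The correlation that reproduces the printed 82 and 76 (about 0.95) gives 74.3 at HR 0.82 and 69.5 at HR 0.83. A WHF correlation of 0.2 with the other statistics lowers these values by at most 0.7 points.

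**Step 3: could another setting make 0.82 give 70?**

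Each candidate breaks a companion row:
- ρ = 0 with WHF HR 0.80 gives 70.1 at 0.82, but 78.4 and 72.0 at 0.80 and 0.816 (printed 82 and 76). It is also implausible, since CV deaths are assumed to be about 80% of all deaths.
- Two-sided alpha 0.04: 71.8% at 0.82, but 73.8% at 0.816 (printed 77).
- 6,375 patients: 72.1% at 0.82, but 74.1% at 0.816.
- 10% fewer events: 70.4% at 0.82, but 79.7% at 0.80 and 72.4% at 0.816.

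**Step 4: the patient number**

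6,800 − 6,375 = 425. Section 1.2 is current text, not part of an amendment log. The Amendment 5 change list names Sections 3.1, 4 and 10.7 for the revised sample size and does not name 1.2. Section 1.2 also leaves WHF out of its efficacy statement, whereas the matching synopsis paragraph includes it. Both point to a missed update.

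**The case against.** The strongest objection is that neither point has consequences for the trial. The sample size rests on CV death alone, all-cause death sits outside the formal multiple testing procedure, and the rows are illustrative scenarios. Section 1.2 is background, and the operative sections agree on 6,800. This is true and limits the weight of the point, but a stated power and a stated sample size that are wrong as printed should still be corrected.

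A second objection is that the table reports gated powers, so ungated figures are the wrong comparison. This matters only for WHF HR 0.80. There the shortfall at 0.82 is about 3 to 4 points rather than 5, and HR 0.83 gives 68.4–69.5%, which is within about a point and a half of the printed 70 but does not always round to it. At the guide correlation of 0.88 it is about 69. The label 0.83 still fits much better than 0.82.

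A third objection is that the sponsor's power output is not in the documents, so 0.82 might have been intended and the 70 be the error. That cannot be strictly excluded. It would require both assumption tables to be wrong as well, and the printed 70 to match 0.83 by coincidence.

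**Conclusion.** Both points hold. The printed 70% is the power at hazard ratio 0.83, the value in the assumption tables, and the label 0.82 is wrong in two rows of each document. At a true hazard ratio of 0.82 the power is 74.9% before the gate, 74.7–74.9% with WHF HR 0.70, and 73.2–74.3% with WHF HR 0.80. The WHF 0.70 result does not depend on the assumed correlation over 0 to 0.95; the WHF 0.80 result assumes a correlation of 0.8 to 0.95 and an independent WHF statistic. Protocol Section 1.2 understates the planned size by 425 patients. No test, stopping boundary, alpha allocation, CV-death power or design size is affected.

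**What to change.** In Protocol Table 10-2 A and SAP Table 2-11 A, change HR=0.82 to HR=0.83 in both affected rows and leave the printed 70. The sponsor can confirm this against its power output. If 0.82 turns out to have been intended, the powers should read about 75 (WHF HR 0.70) and 74 (WHF HR 0.80), and Tables 10-1 and 2-10 would need changing to match. In Protocol Section 1.2, change 6,375 to 6,800. The cost is four table labels and one number; no analysis changes.

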## **11 Ethical considerations**

### **11.1 Regulatory and ethical compliance**

This clinical study was designed and shall be implemented and reported in accordance with the ICH Harmonized Tripartite Guidelines for Good Clinical Practice, with applicable local regulations (including European Directive 2001/20/EC, US Code of Federal Regulations Title 21, and Japanese Ministry of Health, Labor, and Welfare), and with the ethical principles laid down in the Declaration of Helsinki.

### **11.2 Informed consent procedures**

Eligible patients may only be included in the study after providing written (witnessed, where required by law or regulation), IRB/IEC-approved informed consent, or, if incapable of doing so, after such consent has been provided by a legally acceptable representative of the patient. In cases where the patient's representative gives consent, the patient should be informed about the study to the extent possible given his/her understanding. If the patient is capable of doing so, he/she should indicate assent by personally signing and dating the written informed consent document or a separate assent form. Informed consent must be obtained before conducting any study-specific procedures (i.e. all of the procedures described in the protocol). The process of obtaining informed consent should be documented in the patient source documents.

Novartis will provide to investigators in a separate document a proposed informed consent form that complies with the ICH GCP guideline and regulatory requirements and is considered appropriate for this study. Any changes to the proposed consent form suggested by the investigator must be agreed to by Novartis before submission to the IRB/IEC, and a copy of the approved version must be provided to the Novartis monitor after IRB/IEC approval.

Women of child bearing potential should be informed that taking the study treatment may involve unknown risks to the fetus if pregnancy were to occur during the study and agree that in order to participate in the study they must adhere to the contraception requirement for the duration of the study. If there is any question that the patient will not reliably comply, they should not be entered in the study.

